8.5.2. Dose Escalation Halting Criteria

If any of the following criteria are met, escalation to the next planned dose cohort will not proceed until all available study data have been reviewed by the SRC.

- More than 25% of the subjects in the cohort experience an AE, grade 2 or above in the same organ class
- A specific AE increases in severity from one cohort to the next AND the number of subjects reporting that AE (at the higher severity level) in the cohort is the same or greater. An exception would be headaches going from a grade 1 to a grade 2.

8.5.3. Evaluation of Dose Escalation

The SRC must agree unanimously on the following criteria prior to dose escalation:

- A review of all available unmonitored and uncoded safety data from at least 7 subjects per cohort to Day 8, at a minimum, demonstrate that study halting criteria as outlined in Section 9.5.2 have not been met.
- A review of all available unmonitored and uncoded safety data from at least 7 subjects per cohort to Day 8, at a minimum, demonstrate that no safety signals of any nature were observed.

8.6. Safety Oversight

8.6.1. Independent Safety Monitor (ISM)

The ISM is a physician with relevant expertise whose primary responsibility is to provide independent safety monitoring in a timely fashion. The ISM will review SAEs and other AEs as needed and provide an independent assessment.

8.6.2. ICON Medical Monitor

The ICON Medical Monitor (MM) is the clinical site's primary point of contact for eligibility or safety related questions. The ICON MM is responsible for liaising with Ology Bioservices Medical Monitor to ensure that all medical concerns are communicated and will provide any potential pertinent medical communication update to the project team as needed. Can make a recommendation that the SRC be convened to review any safety concerns.

The ICON Medical Monitor will communicate with the Ology Bioservices Medical Monitor for any safety related questions. The ICON MM will participate in the planned SRC meetings and can make a recommendation that the SRC be convened to review any safety concerns.

8.6.3. Ology Bioservices Medical Monitor

The Ology Bioservices Medical Monitor will be the main point of contact for the ICON MM including any safety-related questions or concerns. The Ology Bioservices MM will escalate any medical or safety concerns to the DOD as needed. The Ology Bioservices MM will participate in the planned SRC meetings and can make a recommendation that the SRC be convened to review any safety concerns.

8.6.4. Safety Review Committee (SRC)

The SRC will be composed of:

- PI, or designee
- Ology Bioservices Medical Monitor
- ICON Medical Monitor or designee;

Objective dose-escalation criteria and safety evaluations will be utilized. For Cohorts 1, 2, and 3 the SRC will evaluate unmonitored and uncoded safety and tolerability data for at least 7 subjects out to Day 8 to determine whether dose escalation can occur. If none of the events described in 9.5.1 Study Halting Criteria or in 9.5.2 Dose Escalation Halting Criteria are observed, dose escalation will proceed. Should any of the study halting criteria or dose escalation halting criteria be met, the SRC will meet to evaluate the data and recommend appropriateness of further dosing. The SRC recommendation to advance to the next level will be documented and provided to all the appropriate parties (PI, Ology Bioservices, ICON and DOD) involved with the study.

If 2 or more subjects withdraw prior to Day 8, those subjects need to be replaced to ensure that data for at least 7 subjects is available for review.

If 2 or more subjects withdraw prior to Day 60 or are not compliant with all PK draws through Day 15, they may be replaced.

If more than 2 subjects withdraw following the Day 8 SRC review of safety data, the site will attempt to replace those subjects in that dose group at the time of the next planned cohort.

9. CLINICAL MONITORING

9.1. Site Monitoring Plan

Site monitoring is conducted to ensure that the human subject protection, study and laboratory procedures, study intervention administration, and data collection processes are of high quality and meet sponsor, GCP/ICH and, when appropriate, regulatory guidelines. Site visits may be conducted by an authorized representative of ICON or other regulatory agencies to inspect study data, subjects' medical records, and eCRFs in accordance with ICH guidelines, GCP and the respective local and national government regulations and guidelines.

The investigator will permit authorized representatives of ICON and the respective local and national health authorities to inspect facilities and records relevant to this study, if needed.

A separate monitoring plan, to be developed by ICON, will describe protocol-specific items to be monitored.

10. STATISTICAL CONSIDERATIONS

10.1. Sample Size Considerations

This is a Phase 1 study first in humans with four dosing Cohorts and no formal sample size calculations based on testing a statistical hypothesis were constructed. Four dosing groups of ten each with eight participants assigned the active group and two assigned to the control group are

practical and provide sufficient information for a total sample size of 40 for a Phase 1 trial primarily designed to assess safety. If ten subjects are studied, then the probability of at least one subject experiencing an event of toxicity can range from 0.728 to 0.996 assuming true event rates between 0.15 and 0.5. Additionally, if no events are observed in a cohort of six dosed subjects receiving G03-52-01 the upper bound of an exact 95% confidence interval for the true proportion is 0.46.

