4. STUDY DESIGN

This is a Phase 1, single-center, placebo-controlled, double-blind, dose-escalation study to evaluate the safety and tolerability of G03-52-01 in healthy adults. This is a first-in-human study consisting of four Cohorts of ten subjects each. Each subject will receive a single IM injection of G03-52-01 or placebo.

Table 1: Cohorts

Cohort	Dose of G03-52-01	Number of Subjects
1	10 mg	10 subjects (8 active, 2 placebo)
2	25 mg	10 subjects (8 active, 2 placebo)
3	50 mg	10 subjects (8 active, 2 placebo)
4	100 mg	10 subjects (8 active, 2 placebo)

Schedule for Subjects

Subjects in Cohorts 1-3 will participate in the study for approximately 150 days, including a 28-day screening period, up to 12-hour inpatient stay and approximately 120-day follow-up after study product administration. Subjects will remain at the clinic and not be eligible for discharge until 8 hours after the IM injection. Last follow up visit scheduled at Day 120.

Subjects in Cohort 4 will participate in the study for approximately 210 days, including a 28-day screening period, up to a 12-hour clinic stay and approximately 180-day follow-up after study product administration. Subjects will remain at the clinic and not be eligible for discharge until approximately 8 hours after the IM injection. Last follow up visit scheduled at Day 180.

The end of the study is defined as the date of the last visit of the last subject in the study.

Schedule for Cohorts

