### **3.5 Determination of Sample Size**

This is a Phase 1 study first in humans with four dosing cohorts and no formal sample size calculations based on testing a statistical hypothesis were constructed. Four dosing groups of ten, each with eight participants assigned the active group and two assigned to the control group, are

practical and provide sufficient information for a total sample size of 40 for a Phase 1 trial primarily designed to assess safety.

If ten subjects are studied, then the probability of at least one subject experiencing an event of toxicity can range from 0.728 to 0.996 assuming true event rates between 0.15 and 0.5. Additionally, if no events are observed in a cohort of six dosed subjects receiving G03-52-01 the upper bound of an exact 95% confidence interval for the true proportion is 0.46.

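### The detection probabilities labelled for ten subjects are the values for eight, and the zero-event bound is given for six subjects on active drug when each cohort plans eight

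*Protocol*

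**What the plan says.** Protocol 10.1 states that no hypothesis-based sample size calculation was made and calls the cohort size practical and sufficient for a Phase 1 safety trial. Each dosing group has ten subjects, with "eight participants assigned the active group and two assigned to the control group". Table 1 in Protocol Section 4 gives the same split for all four cohorts, "10 subjects (8 active, 2 placebo"), as does Table 3-1 in SAP 3.1.

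Two figures follow in Protocol 10.1:

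- Detection probability, with p running from 0.15 to 0.5: "If ten subjects are studied, then the probability of at least one subject experiencing an event of toxicity can range from 0.728 to 0.996".
- Zero-event bound, introduced by "if no events are observed in a cohort of six dosed subjects receiving G03-52-01" and given as 0.46 for an exact 95% confidence interval.

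SAP 3.5 repeats both sentences. Its version of the second includes "a cohort of six dosed subjects receiving G03-52-01 the upper bound of an exact 95% confidence interval for the true proportion is 0.46". The SAP revision history records that Section 3.5 was updated for 40 subjects in Final 2.0, so both sentences stand in the current text.

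**The concern.** Three different numbers of subjects appear in one short paragraph: ten as the label of the first figure, eight in the stated design, and six as the label of the second. A reader who computes the first figure from its label does not get the printed values. A reader who wants the bound for a cohort as planned does not find it.

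These two sentences are the only quantitative statement of precision in either document. In a first-in-human trial with safety as the primary objective, they are what supports calling the size sufficient, and they could be carried into the study report. If the labels are wrong, the plan misdescribes what an event-free or event-positive cohort would tell the reader.

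**Working it through.** **Inputs.** True event rates of 0.15 and 0.5, the stated n of ten and the stated n of six come from Protocol 10.1 and SAP 3.5. The planned eight active and two placebo subjects per cohort come from Protocol 10.1, Protocol Table 1 and SAP Table 3-1.

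**Detection probability.** P(at least one event) = 1 − (1 − p)^n.

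| n | p = 0.15 | p = 0.5 |
|---|---|---|
| 6 | 0.623 | 0.984 |
| 7 | 0.679 | 0.992 |
| 8 | 1 − 0.85^8 = 0.7275 | 1 − 0.5^8 = 0.9961 |
| 9 | 0.768 | 0.998 |
| 10 | 1 − 0.85^10 = 0.8031 | 1 − 0.5^10 = 0.9990 |

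The printed pair, 0.728 and 0.996, matches only n = 8. At the stated n = 10 the lower figure is off by 0.803 − 0.728 = 0.075, too much for rounding. The upper figure is off by 0.999 − 0.996 = 0.003.

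**Zero-event bound.** With no events, the exact (Clopper-Pearson) two-sided 95% upper bound is 1 − 0.025^(1/n).

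| n | Upper bound |
|---|---|
| 5 | 0.522 |
| 6 | 0.459 |
| 7 | 0.410 |
| 8 | 0.369 |
| 10 | 0.309 |

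The printed 0.46 is reproduced at n = 6. It is not a one-sided bound for another n: the one-sided 95% form, 1 − 0.05^(1/n), gives 0.393 at n = 6 and 0.312 at n = 8. For the planned eight active subjects the two-sided bound is 0.37, a difference of 0.46 − 0.37 = 0.09.

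**Could six be deliberate?** Protocol 8.5.3 lets the escalation review proceed on "safety data from at least 7 subjects per cohort to Day 8", without saying how many must be active. With at most two placebo subjects in a cohort, seven reviewed subjects include five to seven on active drug, with bounds of 0.52, 0.46 and 0.41. Six is therefore possible at that review, but neither document gives this as the reason. If it were the reason, the matching detection range would be 0.623 to 0.984, and the first sentence would still be on a different n.

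**The case against.** The first sentence does not say that ten subjects receive G03-52-01. The sentence before it defines a group of ten with eight on active drug, so it could be read as describing a ten-subject cohort and the chance of an event among its eight active members. On that reading the values are right and only the wording is loose. This is plausible as the origin of the figures, but the sentence names ten as its n and does not restrict the event to active subjects, as the next sentence does. It still needs the word eight.

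The second figure is not a miscalculation. It is conditional, correct for its stated n, and errs in the cautious direction. All of that stands. The fault is the missing link to the planned cohort.

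Six might also come from the replacement rules. Under Protocol 4.2.1 and 8.6.4, the attempt to replace subjects lost after the Day 8 review begins only when more than two are lost, so two losses from eight active would leave six. But the sentence counts dosed subjects, and later withdrawal does not reduce that count. The documents do not make the connection either.

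Finally, nothing operational depends on these figures. That is true and keeps the point minor.

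**Conclusion.** The concern holds, as a minor error in stated figures. The range 0.728 to 0.996 is wrong for ten subjects (0.803 to 0.999) and right for eight. The bound of 0.46 is right for six, but the planned eight active subjects give 0.37, 9 percentage points lower, and no section explains six.

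Both discrepancies understate what the study can show: detection probability for the stated ten is higher than printed, and the bound for the planned eight is tighter. Halting rules, escalation rules, the total of 40 and the planned descriptive analyses are unaffected.

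The calculation assumes independent events at a common rate within a cohort, and reads the exact interval as two-sided Clopper-Pearson, which is the form that reproduces the plan's own 0.46.

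**What to change.** Revise the two sentences in Protocol 10.1 and make the same change in SAP 3.5. Suggested text:

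> With eight subjects on G03-52-01 in a cohort, the chance of seeing at least one toxicity is 0.728 at a true rate of 0.15 and 0.996 at a true rate of 0.5. Should none of these eight have a toxicity, the exact two-sided 95% upper limit for the true rate is 0.37.

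If six was meant as a reduced-cohort case, say so, state how it arises, and keep 0.46 beside the figure for eight.

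The cost is two sentences in each document. Design, sample size, conduct and planned analyses do not change.

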4.2 Treatment Assignment Procedures

4.2.1 Randomization Procedures

Randomized treatment assignments will be generated by a statistician at ICON PLC. Randomization will occur following admittance to the unit and confirmation of eligibility is confirmed.

This is a Phase 1 double-blinded, placebo-controlled trial that will randomize subjects within four dosing Cohorts to either active or placebo in an overall 4:1 ratio. For each dosing cohort, the first two subjects will be randomized in a 1:1 fashion to active and placebo to ensure that one of the first two subjects receives active treatment and the other control. An alternate subject will be admitted to the unit for each two-subject group. If one of the first two subjects is not randomized for any reason, then the alternate subject will receive the next consecutive randomization number. The product assignment of the remaining eight subjects in each cohort will be a simple random sample to ensure the 4:1 ratio for the dosing cohort. The randomization list will be generated by the unblinded study biostatistician and transferred to the unblinded study pharmacist prior to start of the study.

If 2 or more subjects withdraw, are lost to follow up or terminate prior to Day 8, those subjects need to be replaced to ensure that data for at least 7 subjects is available for review.

If 2 or more subjects withdraw, are lost to follow up or terminate prior to Day 60 or are not compliant with all PK draws through Day 15, they may be replaced.

If more than 2 subjects withdraw, are lost to follow up or terminate following the Day 8 SRC review of safety data, the site will attempt to replace those subjects in that dose group at the time of the next planned cohort.

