4.2.4 Handling of Withdrawals

Subjects who are withdrawn prior to dosing may be replaced. Following dosing, one subject per cohort may withdraw prior to the completion of Visit 11 (Day 60) or was noncompliant with all PK draws through Visit 6 (Day 4) without being replaced. Should more than one subject from the same cohort voluntarily withdraw from the study who did not meet the above criteria, those subjects may be replaced. Subjects who withdraw or are withdrawn from the study who received any amount of the study product will be encouraged to continue follow-up (with subjects' consent) for safety. Subjects withdrawing will be asked to complete a final termination visit if they do not wish to be followed per protocol.

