### **3.4 Randomization and Treatment Assignments**

Eligible subjects will be randomly assigned to study drug G03-52-01 within four dosing cohorts to either active or placebo in an overall 4:1 ratio. For each dosing cohort, the first two subjects will be randomized in a 1:1 fashion to active and placebo to ensure that one of the first two subjects receives active treatment and the other control. An alternate subject will be admitted to the unit for each two-subject group. If one of the first two subjects is not randomized for any reason, then the alternate subject will receive the next consecutive randomization number. The product assignment of the remaining eight subjects in each cohort will be a simple random sample to ensure the 4:1 ratio for the dosing cohort.

Randomized treatment assignments will be generated by a statistician at ICON PLC. Randomization will occur following admittance to the unit and confirmation of eligibility is confirmed. The randomization list will be generated by the unblinded study biostatistician and transferred to the unblinded study pharmacist prior to start of the study.

If 2 or more subjects withdraw, are lost to follow up or terminate prior to Day 8, those subjects need to be replaced to ensure that data for at least 7 subjects is available for review.

If 2 or more subjects withdraw, are lost to follow up or terminate prior to Day 60 or are not compliant with all PK draws through Day 15, they may be replaced.

If more than 2 subjects withdraw, are lost to follow up or terminate following the Day 8 SRC review of safety data, the site will attempt to replace those subjects in that dose group at the time of the next planned cohort.

The detailed randomization scheme and distribution list will be described in the randomization plan.

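### Protocol 10.1 and SAP 3.5 label the detection range as ten subjects when it is the result for eight, and give the zero-event bound for six; each cohort plans eight recipients (minor)

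*Protocol*

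**What the plan says.** Protocol section 4, Table 1, describes every cohort as "10 subjects (8 active, 2 placebo"), and the opening of section 10.1 repeats that split. Section 10.1 says that no formal hypothesis-based calculation was made. It then supports the cohort size with two figures:

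- Chance of seeing an event: "If ten subjects are studied, then the probability of at least one subject experiencing an event of toxicity can range from 0.728 to 0.996", for true rates from 0.15 to 0.5.
- Bound when nothing is seen: "in a cohort of six dosed subjects receiving G03-52-01 the upper bound of an exact 95% confidence interval for the true proportion is 0.46".

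SAP 3.5 carries the same two sentences with the same numbers.

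**The concern.** Two adjacent sentences describe one cohort, one for ten subjects and the other for six. Neither names the eight recipients that the design provides. The ten would include two placebo subjects, who carry no information about drug toxicity. The six matches no planned group.

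These are the only figures in either document that say what a cohort can show, and safety is the primary objective. SAP 7.22 tabulates safety by dose level with placebo pooled across cohorts, so a full cohort with no events of a given kind will be reported as 0 of 8. A reader who wants the matching bound will find only the one for six. A reader who recalculates the detection range at the stated ten will not reproduce it. At stake is the accuracy of the stated justification, not the design.

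**Working it through.** **Inputs.** Printed range 0.728 to 0.996, stated for ten subjects, with true rates 0.15 and 0.5; printed bound 0.46, stated for six recipients, exact 95% (Protocol 10.1 and SAP 3.5). Planned recipients per cohort: 8 (Protocol section 4, Table 1).

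**Formulas.** With n independent subjects and true rate p, the probability of at least one event is 1 − (1 − p)^n. With zero events in n, the upper limit of the exact (Clopper-Pearson) two-sided 95% interval is 1 − 0.025^(1/n).

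**Step 1: the printed range at the stated n.** For n = 10:

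- p = 0.15: 1 − 0.85^10 = 0.803
- p = 0.5: 1 − 0.5^10 = 0.999

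The lower end differs from the printed 0.728 by 0.075, so the range is not reproduced. To obtain 0.728 with ten subjects, the true rate would have to be about 0.122 rather than 0.15.

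**Step 2: the n that gives the printed range.** For n = 8:

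- p = 0.15: 1 − 0.85^8 = 0.7275, printed as 0.728
- p = 0.5: 1 − 0.5^8 = 0.9961, printed as 0.996

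Both ends match to three decimals. None of the other sizes checked (5, 6, 7 and 10) gives this pair.

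**Step 3: the printed bound.** For n = 6, 1 − 0.025^(1/6) = 0.459, which reproduces 0.46. The one-sided 95% version, 1 − 0.05^(1/6) = 0.393, does not, so the printed figure is the two-sided bound for six. For n = 8, 1 − 0.025^(1/8) = 0.369. The difference is 0.459 − 0.369 = 0.09.

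| n | What it represents | At least one event, p = 0.15 | At least one event, p = 0.5 | Zero-event upper bound |
|---|---|---|---|---|
| 6 | stated for the bound | 0.623 | 0.984 | 0.46 |
| 8 | planned recipients | 0.728 | 0.996 | 0.37 |
| 10 | stated for the range; includes 2 placebo | 0.803 | 0.999 | 0.31 |

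The printed range belongs to the row for eight and the printed bound to the row for six. No single row contains both.

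**The case against.** The strongest reply is that nothing is overstated. Just before these figures, section 10.1 says that eight of the ten receive active product, and 0.728 to 0.996 is the correct chance of seeing an event among those eight. The sentence with 0.46 names its own sample size, is correct for it, and is conservative for eight. No analysis or decision rule uses either number. All of this stands and is why the point is minor. It does not remove the error: the first sentence attaches its result to the wrong number of subjects, and the second describes a cohort that the plan does not contain. One might suppose that six allows for losses, but neither document says so.

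A reader might infer more from the safety review rules. The documents do not support these stronger readings:

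- **Escalation on too few recipients.** Protocol 8.5.3 asks for "safety data from at least 7 subjects per cohort to Day 8, at a minimum" and names no arm. With two placebo subjects, seven could include only 7 − 2 = 5 recipients. But section 8.6.4 ties the quorum, "safety and tolerability data for at least 7 subjects out to Day 8 to determine whether dose escalation can occur", to Cohorts 1, 2 and 3. Those escalations appear to be past: section 2.2 reports that the step to 100 mg was decided on the Day 60 interim, which section 10.2 says covers Cohorts 1-3. No dose above Cohort 4 is planned. Unanimity of the Safety Review Committee (SRC) and the halting rules apply at any count.
- **Conflicting replacement rules.** Section 4.2.4 says "those subjects may be replaced", which might seem to contradict the Day 8 rule in 4.2.1, "those subjects need to be replaced to ensure that data for at least 7 subjects is available for review". The 4.2.4 rule concerns Day 60 and PK draws, however, and its counterpart in 4.2.1, the Day 60 and PK sentence, is also permissive. The Day 8 rule is a separate one and is already mandatory.
- **Active subjects replaced by placebo.** Neither document says which arm a replacement takes, but SAP 3.4 states: "The detailed randomization scheme and distribution list will be described in the randomization plan". That plan is not among the documents, so silence here does not show a gap.
- **An ambiguous 25% rule.** Section 8.5.2 refers to the cohort's subjects, and Table 1 defines a cohort as ten.

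**Conclusion.** Wrong as written, and minor. The range 0.728 to 0.996 is labelled as ten subjects but is the result for eight; for ten it would be 0.803 to 0.999. The bound of 0.46 is right for six recipients, but every cohort plans eight, for which it is 0.37.

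The result follows from the binomial formula and the exact interval, with independent subjects and a common event rate within a cohort; no outside figure is needed. It assumes eight dosed and evaluable recipients, as planned. It does not show that the cohorts are too small, that the chance of detection was inflated for the planned recipients, or that any escalation was unsafe.

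**What to change.** In Protocol 10.1 and SAP 3.5, replace the two sentences with:

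> With eight G03-52-01 recipients per cohort, the probability that at least one has an event is 0.728 to 0.996 for true event rates of 0.15 to 0.5. If none of the eight has an event, the upper bound of the exact two-sided 95% confidence interval is 0.37.

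This removes the references to ten subjects and to six recipients. It is a wording change only: the total stays at 40, and all analyses and decision rules are unchanged.

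No change to the quorum, replacement or 25% rules is proposed. In particular, asking an unblinded party to confirm to the SRC that at least seven active subjects were reviewed could reveal assignments to a committee that includes the investigator. As an option, the study report could state how many G03-52-01 recipients had Day 8 data at each past SRC review.
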